### 8.3 Clinical laboratory evaluations

Hematology, blood chemistry (including liver function tests), urinalysis, and endocrinology parameters are assessed throughout the study, according to the tabular schedules of study procedures. Urinalysis will be performed for study participants  $\geq 5$  years of age only.

All summaries of laboratory parameters will only summarize parameters planned based on the protocol. However, both planned and unplanned laboratory parameters will be provided in subject data listings. Summaries will include hematology, chemistry and endocrinology results; urinalysis results will be included in subject data listings only.

Observed values of hematology, chemistry, and non-gender specific endocrinology parameters (ie, thyroid stimulating hormone, triiodothyronine [total and serum-free], and thyroxine [total and serum-free]) will be summarized for each visit and Last Visit. Change from Baseline for hematology, chemistry, and non-gender specific endocrinology parameters will be summarized for all post-Baseline visits, and Last Visit. Gender specific endocrinology parameters (ie, follicle stimulating hormone, luteinizing hormone, and testosterone) will be presented similarly, by gender.

A shift table that cross-tabulates Baseline versus maximum result during the Treatment Period in categories of  $<1 \times \text{ULN}$  (upper limit of normal),  $1$  to  $<2 \times \text{ULN}$ ,  $2$  to  $<3 \times \text{ULN}$ ,  $\geq 3 \times \text{ULN}$ , and missing will be presented for liver function tests (LFT) which include Alanine Aminotransferase (ALT), Aspartate Aminotransferase (AST), Gamma-glutamyl Transferase (GGT), Total Bilirubin, and Alkaline Phosphatase.

Treatment-emergent markedly abnormal (TEMA) values are defined as those TEMA values during the defined Treatment Period at scheduled or unscheduled visits which occur on or after the first SP848 LCM administration through to the end of the study but were normal at Baseline. The age at the time of assessment will be used for determining TEMA. The age at the time of visit/assessment will be obtained using date of informed consent to date of visit.

The number and percentage of study participants with a TEMA value, TEMA low value, and TEMA high value will be summarized, at each post-Baseline visit and Last Visit. Percentages will be relative to the number of study participants with a value at each time point. Criteria for determining if a value is TEMA are detailed in Appendix 12.1.

Serum and urine pregnancy testing will be performed on all females of childbearing potential, according to the tabular schedule of study procedures. Serum and urine pregnancy test results will be listed. No summaries of these results are planned.

PDILI IMP discontinuation criteria as outlined in the protocol, will be evaluated at all laboratory assessments. The number and percentage of study participants meeting PDILI criteria (ie, ALT or AST criteria and/or total bilirubin criteria, and/or presence of symptoms), will be presented by treatment group. Percentages will be based on the number of study participants with a non-missing measurement for the variable of interest at the relevant visit.

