## **8.4 Vital signs, physical findings, and other observations related to safety**

### **8.4.1 Vital signs, body weight, height, and BMI**

Vital signs (systolic blood pressure [SBP], diastolic blood pressure [DBP], pulse rate, and temperature), body weight, and height will be collected according to the tabular schedule of study procedures. In addition, BMI will be calculated (as defined in Section 3.2.11) for each visit where weight and height are collected.

Noninvasive blood pressure (systolic and diastolic) and pulse rate will be measured at all visits in a sitting position after at least 3 minutes at rest. Body weight will be determined without shoes and wearing light clothing. Height will be measured without shoes.

All summaries of vital signs, body weight, height, and BMI will only summarize variables planned based on the protocol. However, both planned and unplanned variables will be provided in subject data listings.

Observed values of SBP, DBP, pulse rate, temperature, body weight, height, and BMI will be summarized for each visit and Last Visit. Change from Baseline for SBP, DBP, pulse rate, temperature, body weight, height, and BMI will be summarized for all post-Baseline visits, and Last Visit.

Markedly abnormal (MA) values are defined as those MA values during the defined Treatment Period at scheduled or unscheduled visits which occur on or after the first SP848 LCM administration through to the end of the study.

The number and percentage of study participants with a MA value, MA low value, and MA high value, at each post-Baseline visit and Last Visit, for which SBP, DBP, pulse rate, temperature, and body weight were scheduled to be assessed, and Last Visit, will be presented. Percentages will be relative to the number of study participants with a value at each time point.

The abnormal vital sign criteria are defined as follows:

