The number and percentage of study participants with treatment-emergent ECG abnormalities will be presented for each post-Baseline visit and Last Visit. Abnormalities reported at an unscheduled visit will be summarized under the scheduled visit preceding the unscheduled visit (if the abnormality was not present already at the preceding scheduled visit). Treatment-emergent is defined as meeting the criteria at any post-Baseline visit during the Treatment Period (including unscheduled visits) and not meeting the same criteria during Baseline. The age at the time of visit/assessment will be used for determining abnormality criteria. The age at the time of assessment will be obtained using date of informed consent to date of visit. All ECG parameter values will be listed for study participants meeting any abnormality criteria.

Abnormality criteria to be used in the determination of ECG abnormalities are defined as follows, where increase and decrease are relative to Baseline values:

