## 12 APPENDICES

### 12.1 Marked abnormality criteria for laboratory data

#### 12.1.1 Marked abnormality criteria for hematology data

**Table 12–1: Hematology abnormality criteria**

Parameter	Age Range	Unit (conventional)	Abnormality criteria (conventional unit)	Unit (standard)	Abnormality criteria (standard unit)
Hematocrit	<2y	%	≤27 >45	%	≤27 >45
	2y - <17y	%	≤29 >47	%	≤29 >47
	≥17y	%	≤85% of LLN ≥115% of ULN	%	≤85% of LLN ≥115% of ULN
Hemoglobin	<2y	g/dL	≤9.0 >15.0	g/L	≤90 >150
	2y - <17y	g/dL	≤9.5 >16.0	g/L	≤95 >160
	≥17y	g/dL	≤85% of LLN ≥115% of ULN	g/L	≤85% of LLN ≥115% of ULN
WBC/ Leukocytes	All	10  /L	≤3.0 ≥16.0	G/L	≤3.0 ≥16.0
Lymphocytes Absolute	<2y	10  /L	<1.0 >9.8	G/L	<1.0 >9.8
	2y - <6y	10  /L	<0.7 >6.9	G/L	<0.7 >6.9
	≥6y	10  /L	<0.6 >5.0	G/L	<0.6 >5.0
Basophils	>1m	%	≥5.0	%	≥5.0
Basophils Absolute	>1m	10  /L	≥0.4	G/L	≥0.4
Eosinophils	>1m	%	≥10	%	≥10
Eosinophils Absolute	>1m	10  /L	≥1.0	G/L	≥1.0
Monocytes	>1m	%	≥20.0	%	≥20.0

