**12.1.2 Marked abnormality criteria for chemistry data**

**Table 12–2: Chemistry abnormality criteria**

Parameter	Age Range	Unit (conventional)	Abnormality criteria (conventional unit)	Unit (standard)	Abnormality criteria (standard unit)
AST (SGOT)	All	U/L	≥3.0 x ULN ≥5.0 x ULN ≥10.0 x ULN	U/L	≥3.0 x ULN ≥5.0 x ULN ≥10.0 x ULN
ALT (SGPT)	All	U/L	≥3.0 x ULN ≥5.0 x ULN ≥10.0 x ULN	U/L	≥3.0 x ULN ≥5.0 x ULN ≥10.0 x ULN
Alkaline Phosphatase	<4y	U/L	≥690	U/L	≥690
	4y - <10y	U/L	≥834	U/L	≥834
	10y - <17y	U/L	≥1761	U/L	≥1761
	≥17y	U/L	≥3.0 x ULN	U/L	≥3.0 x ULN
GGT	<6m	U/L	≥522	U/L	≥522
	6m - <1y	U/L	≥279	U/L	≥279
	1y - <13y	U/L	≥66	U/L	≥66
	13y - <17y	U/L	≥126	U/L	≥126
	≥17y	U/L	≥3.0 x ULN	U/L	≥3.0 x ULN
Total Bilirubin	>1m	mg/dL	≥2.0	umol/L	≥34.208
Total Protein	2m-<1y	g/dL	<3.0 >11.9	g/L	<30 >119
	1y - <17y	g/dL	<4.3 >12.0	g/L	<43 >120
	≥17y	g/dL	<4.3 >13.0	g/L	<43 >130
Albumin	<1y	g/dL	<1.6 >7.2	g/L	<16 >72
	≥1y - <17y	g/dL	<2.4 >8.4	g/L	<24 >84
	≥17y	g/dL	<2.6	g/L	<26
BUN	<1y	mg/dL	≥24	mmol/L	≥8.568
	1y - <17y	mg/dL	≥36	mmol/L	≥12.852

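### The laboratory TEMA rule requires a normal Baseline, so participants with a mildly abnormal or missing Baseline cannot enter the TEMA tables but stay in the denominator

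*SAP*

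**What the plan says.** Section 8.3 of the SAP defines laboratory TEMA values as marked values in the Treatment Period "which occur on or after the first SP848 LCM administration through to the end of the study but were normal at Baseline". It then says "Criteria for determining if a value is TEMA are detailed in Appendix 12.1", and for the by-visit counts of TEMA, TEMA low and TEMA high it says "Percentages will be relative to the number of study participants with a value at each time point".

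Appendix 12.1 sets marked limits only. It does not say what *normal* means. Two examples show how far the limits lie from normal:

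- AST and ALT, all ages (Table 12–2): "≥3.0 x ULN ≥5.0 x ULN ≥10.0 x ULN".
- Hematocrit and hemoglobin from 17 years (Table 12–1): "≤85% of LLN ≥115% of ULN".

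The other safety sections use different rules:

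- **ECGs (Section 8.4.2):** treatment-emergent means "meeting the criteria at any post-Baseline visit during the Treatment Period (including unscheduled visits) and not meeting the same criteria during Baseline".
- **Vital signs (Section 8.4.1):** there is no Baseline condition in the general definition: "Markedly abnormal (MA) values are defined as those MA values during the defined Treatment Period at scheduled or unscheduled visits".

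**The concern.** Between the edge of normal and the marked limit lies a band of values that are abnormal but not marked. A Baseline in that band is not normal, so the Section 8.3 condition fails and no later marked value from that participant can count. A missing Baseline fails in the same way, because it cannot be shown to be normal.

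The rule also ignores direction. A white cell count above the laboratory's range at Baseline but below the marked limit of 16.0, later falling to 3.0 or less, would not be a TEMA low.

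The excluded participants still have values at the visit, so they remain in the denominator. Long-term safety comes first among the objectives in Section 2.1, and the TEMA tables are the only planned incidence summaries built on the Appendix 12.1 criteria. Their error runs one way, towards too few events.

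**Working it through.** The SAP states no figure on this point, so there is none to reproduce. The check applies the written rule and the ECG-type rule to the same values, then does the algebra.

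**1. Two rules, same ALT values.** Marked means at least 3 x ULN (Table 12–2). *Written rule*: Baseline no higher than ULN and later value marked. *ECG-type rule*: Baseline below 3 x ULN and later value marked.

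| Baseline (x ULN) | On treatment (x ULN) | Written rule | ECG-type rule |
|---|---|---|---|
| 0.8 | 3.2 | counted | counted |
| 1.5 | 3.2 | not counted | counted |
| 2.9 | 10.5 | not counted | counted |
| 3.1 | 3.5 | not counted | not counted |

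The rules differ only where the Baseline is abnormal but not marked.

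**2. Direction of the bias.** If each marked limit lies outside the reference range, everyone counted by the written rule is also counted by the ECG-type rule. The denominator is the same, so the written percentage cannot exceed the other. The condition holds by construction for limits set as multiples of ULN or LLN. It is assumed for the absolute limits, because the SAP gives no reference ranges.

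**3. Size.** Let b be the fraction with a non-normal, non-marked Baseline, p0 the risk of a marked value from a normal Baseline, and p1 the risk from the b group. Missing and already marked Baselines are left out for simplicity.

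- Counted as written: N(1 − b)p0
- All new marked abnormalities: N[(1 − b)p0 + b·p1]
- Share lost: b·p1 / [(1 − b)p0 + b·p1], which equals b when p1 = p0

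The documents give none of b, p0 or p1, so the values below are assumptions. N = 400 is the approximate maximum in Section 2.5; it cancels in the share lost. p0 is set at 2%.

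| b | p1 | Counted as written | All new | Share lost |
|---|---|---|---|---|
| 5% | 2% | 7.6 (1.9%) | 8.0 (2.0%) | 5.0% |
| 10% | 2% | 7.2 (1.8%) | 8.0 (2.0%) | 10.0% |
| 10% | 10% | 7.2 (1.8%) | 11.2 (2.8%) | 35.7% |
| 20% | 10% | 6.4 (1.6%) | 14.4 (3.6%) | 55.6% |
| 20% | 20% | 6.4 (1.6%) | 22.4 (5.6%) | 71.4% |

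For the third row: 400 × 0.9 × 0.02 = 7.2; 400 × 0.1 × 0.1 = 4.0; 4.0 / 11.2 = 35.7%.

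**4. Age bands, which any new rule must handle.** Section 8.3 applies the criteria at the age of assessment. GGT is marked at 522 U/L below 6 months and at 66 U/L from 1 to under 13 years.

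- GGT 300 before 6 months, then 70 after the first birthday. If the Baseline is judged at the Baseline age, 300 < 522 is not marked and 70 ≥ 66 is, so a TEMA arises although the value fell. If the Baseline is judged by the later band, 300 ≥ 66 is already marked and no TEMA arises.
- GGT 100 before 6 months, then 500 after the first birthday. Judged at the Baseline age this is a TEMA. Judged by the later band, 100 ≥ 66 is already marked and a fivefold rise is lost.

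Neither choice is harmless by itself, so the plan has to state one.

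**The case against.** **The values are not hidden.** This stands, and it limits the point. All values are listed, and observed values and changes from Baseline are summarized by visit. For ALT, AST, GGT, total bilirubin and alkaline phosphatase, the Section 8.3 shift table has no normal-Baseline condition and includes a missing category. An ALT rising from 1.2 to 11 x ULN appears there, and may also appear in the PDILI count or as a reported event in Table 12–4. A reader might infer that such a liver signal disappears from the report; the documents do not support that.

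The cover is partial. The shift table stops at 3 x ULN or more, so it cannot show the 5 and 10 x ULN levels. It does not reproduce the absolute limits for bilirubin, or for GGT and alkaline phosphatase below 17 years. Hematology, renal, electrolyte, lipid and other parameters have no equivalent incidence summary.

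**Normal may mean not markedly abnormal.** The term is undefined, and on that reading the mildly abnormal Baselines would be counted. But the SAP says this nowhere, its ECG rule shows that it can express that condition, and Section 8.3 itself uses normal in the sense of the upper limit of normal. If the lenient reading was meant, the sentence still needs changing.

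**The stakes are modest.** Partly right. All summaries are descriptive, and laboratory parameters are listed in Section 2.3.2 among the other safety variables, not the primary ones. No planned analysis compares laboratory with ECG rates, so the different rules invalidate no comparison. The denominator matches the one used for vital signs, and keeping it is defensible.

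**Conclusion.** As written, Section 8.3 bars participants with a mildly abnormal or missing Baseline from the TEMA numerator while keeping them in the denominator, and so departs from the SAP's own ECG rule. Provided the marked limits lie outside the reference ranges, TEMA percentages can only be too low. The loss is confined to the TEMA tables and matters most for the non-liver parameters.

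The size cannot be computed from the documents. At equal risk it equals b. Under the assumed ranges (b from 5% to 20%, p0 of 2%, p1 from 2% to 20%), 5% to 71% of new marked abnormalities are missed, or 0.1 to 4.0 percentage points (b·p1). A reader might take one of these figures as the expected loss, or suppose that participants on other AEDs often start outside the reference range. The documents give no rates to support either.

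**What to change.** Replace the defining sentence in Section 8.3, which also defines TEMA by reference to itself, with a rule containing these elements:

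- A TEMA value is a value on or after the first SP848 dose, within the Treatment Period, that meets an Appendix 12.1 criterion for the participant's age at that assessment. The Baseline value must not have met the corresponding marked criterion in the same direction and at the same level.
- The Baseline value is classified by the criterion for the participant's age at Baseline, or the plan states the alternative it prefers. Because that choice alone does not prevent the first GGT case above, add a condition: where the age band has changed and the value has moved no further in the criterion's direction than at Baseline, show the case as a change of age band and not as a TEMA.
- Participants with a missing Baseline and a marked value on treatment are reported as a separate count.

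The cost is a rewritten definition and a changed derivation flag, with no new data. Reported TEMA percentages would be higher, by an amount that depends on how many participants start outside normal.

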### 3.2.4 Study visit labeling

Visits will be labeled in table summaries (according to the schedule outlined in Section 16.1 of the protocol) as follows:

- “Screening Visit” for study participants who directly enrolled into SP848
- “Titration Visit X” for scheduled visits during titration for study participants who directly enrolled into SP848
- “Visit X, Week X” for other scheduled visits during the Treatment Period
- “Last Visit” (see below in Section 3.2.6 for further information)

Listings will also include “Unscheduled Visit” as applicable.

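### Marked laboratory and vital-sign abnormalities at unscheduled visits enter the TEMA/MA tables only as the Last Visit value, and no any-time count is planned beyond the liver-test shift table

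*SAP*

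**What the plan says.** For laboratory data, Section 8.3 defines TEMA values as those arising "at scheduled or unscheduled visits which occur on or after the first SP848 LCM administration through to the end of the study", provided the parameter was normal at Baseline. Section 8.4.1 defines MA vital-sign values over the same range of visits, without the Baseline condition.

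The tabulation is narrower. Section 8.3 states: "The number and percentage of study participants with a TEMA value, TEMA low value, and TEMA high value will be summarized, at each post-Baseline visit". It plans the same counts for Last Visit, and adds: "Percentages will be relative to the number of study participants with a value at each time point". Section 8.4.1 plans "The number and percentage of study participants with a MA value, MA low value, and MA high value, at each post-Baseline visit and Last Visit", and ties those visits to ones at which the vital sign was due to be measured.

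Section 3.2.4 gives tables labels for Screening, titration visits, numbered visits and Last Visit. It then says: "Listings will also include “Unscheduled Visit” as applicable".

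For ECGs, Section 8.4.2 closes the same gap with an explicit rule: "Abnormalities reported at an unscheduled visit will be summarized under the scheduled visit preceding the unscheduled visit". Sections 8.3 and 8.4.1 have no such rule.

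**The concern.** The definition and the tables do not cover the same values. The definition takes in unscheduled visits, while the tables offer them no place except the Last Visit entry. When an abnormal value is followed by a later on-treatment value, for instance a recheck, the words about unscheduled visits have no effect on the TEMA/MA tables.

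There is a second, related gap. A reader of long-term safety data wants to know how many children had at least one marked abnormality in a given parameter while on treatment. By-visit rows cannot answer that, because the same child may appear in several rows or in only one. Adverse events do get such a count: Section 8.2 counts participants who experience each event at least once. For most laboratory parameters and all vital signs, no equivalent is planned. Long-term safety is part of the first-listed objective in Section 2.1.

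**Working it through.** The SAP states no figure on this point, so the check is to follow an abnormal value through the rules.

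**Where a marked abnormality goes**

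1. *Found at a scheduled visit.* It enters that visit's row (8.3, 8.4.1).
2. *Found at an Early Termination Visit.* Section 3.2.3 maps it to a scheduled visit, so it is kept.
3. *Found at an unscheduled visit, with no later on-treatment value of that parameter.* Section 3.2.6 takes Last Visit as the last non-missing assessment in the Treatment Period and considers unscheduled ones. The value enters the Last Visit row.
4. *Found at an unscheduled visit, with a later on-treatment value.* Last Visit takes the last value, not the worst, so the later one is used. There is no unscheduled label in tables (3.2.4) and no mapping rule. The value enters no TEMA/MA cell.
5. *As in case 4, but for ALT, AST, GGT, total bilirubin or alkaline phosphatase.* The shift table in 8.3 uses the maximum result over the Treatment Period, and its wording does not exclude unscheduled values. The value can appear there.

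Example of case 4: a child's absolute neutrophil count falls below the 1.5 limit of Table 12–1 at an unscheduled visit and is normal at the next scheduled one. The child meets the TEMA definition if normal at Baseline, but is counted as TEMA in no row.

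**What the liver shift table leaves open**

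Its top category is ≥3 x ULN. Table 12–2 sets ALT and AST limits at ≥3, ≥5 and ≥10 x ULN, so the two higher levels are not separated. Table 12–2 also gives fixed limits in U/L for GGT and alkaline phosphatase by age below 17 years, which the ULN categories do not reproduce. The table covers no hematology, electrolyte or vital-sign parameter.

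**Why by-visit rows do not give an any-time figure**

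Suppose each of k assessments has abnormality rate p in the same participants. The share ever affected then lies between p (the same children every time) and k × p (different children each time), with 1 − (1 − p)^k under independence. As an illustration only, with p, k and independence all assumed:

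| p per visit | k = 7 | k = 13 |
|---|---|---|
| 0.5% | 1 − 0.995^7 = 3.4% | 1 − 0.995^13 = 6.3% |
| 1% | 1 − 0.99^7 = 6.8% | 1 − 0.99^13 = 12.2% |

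If the same children are abnormal every time, these figures fall back to 0.5% and 1%. The table shows only that per-visit and any-time percentages can differ widely. It does not measure how many abnormalities are lost at unscheduled visits.

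**The case against.** Several stronger readings suggest themselves, and the SAP does not support them.

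- *Unscheduled abnormalities reach no table, or are shown as zero.* Section 3.2.6 draws Last Visit from unscheduled assessments too, so those that are the last value are tabulated. The others are not assigned to a cell, which is different from being reported as zero.
- *No ever-on-treatment summary exists.* The liver shift table is one, within the limits shown above.
- *The ECG table has the same defect, or lacks a matching denominator.* ECGs have a mapping rule. The denominator of participants with an ECG at the visit belongs to the summary of normal, abnormal and clinically significant findings. The treatment-emergent ECG table states no denominator, so that argument cannot be built on it.
- *Extra visits are where symptomatic children are seen, so the worst events are removed.* The SAP does not say why unscheduled visits occur. Nothing is removed from the report: Section 3.1 plans listings of all documented data, and Section 8.4.1 adds a separate listing of MA vital signs.

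Three further points on the other side carry weight. The laboratory sentence does not itself say scheduled visits; that restriction follows from the labels in 3.2.4 and is explicit only for vital signs. Laboratory values and vital signs are other, not primary, safety variables (2.3.1, 2.3.2). All summaries are descriptive.

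These points limit the importance of the gap but do not close it. If the laboratory sentence was meant to include unscheduled visits, the SAP still lacks a rule for placing them. A listing gives no incidence.

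**Conclusion.** The point holds in limited form. An unscheduled marked abnormality is tabulated as TEMA or MA only if it is the participant's last on-treatment value; otherwise it is found only in listings, or for the five liver tests possibly also in the shift table. Outside that shift table, no count of participants with at least one TEMA or MA value during treatment is planned.

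The conclusion rests on reading 3.2.4 as the full set of table labels and, for laboratory values, as limiting the rows to scheduled visits. The size of the effect cannot be derived from the SAP, since it depends on how many unscheduled values are abnormal and followed by another value. What is certain is the direction: in the same participants, the any-time percentage cannot be below that of any single visit. The change is worth making because it is cheap and aligns the tables with the SAP's own definitions. It does not affect the primary safety variables.

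**What to change.** In the TEMA tables of Section 8.3 and the MA table of Section 8.4.1, add a row for values at any time during the Treatment Period, scheduled or unscheduled. Give it for any, low and high values and count each participant once. Use as denominator the participants with at least one post-first-dose value of that parameter. Keep the by-visit and Last Visit rows.

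For consistency, the same row may be added to the treatment-emergent ECG table in 8.4.2 and to the PDILI count in 8.3, where criteria are evaluated at every laboratory assessment but percentages refer to the relevant visit.

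The cost is a change of SAP wording and one extra row per table, with no new data. The any-time percentages may be higher than the by-visit ones, so the row should be labelled clearly. Which row the report emphasizes is the sponsor's choice.
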